2.2. End-points

- Mortality
- Overall survival (OS)
- Quality of Life (QoL)
- Cost-effectiveness

3. Patient selection criteria

3.1. Patients inclusion criteria

Inclusion criteria:

- current or former smoker status;
- for former smokers, the maximum time since quitting smoking below 10 years.
- smoking history of at least 20 pack-years;
- age 45-75 years;

- no previous history of cancer in the 10 years before the start of the study;
- be able to stand and hold the breath for 11 seconds during image acquisition
- previous participation to SOS trial

3.2. Exclusion criteria

[figure not shown]
Exclusion criteria:

- pregnancy

4. Trial Design

During this study, about 1700 subjects, who have been enrolled in SOS Observational Study will undergo a DTS. The study will be presented as an observational clinical trial and registered on clinicaltrials.gov. Initially, all the subjects that participated in the SOS study, will be contacted by phone and invited to perform a DTS in Carle Hospital. When accessing the hospital the subjects will be asked to fill-in a form to confirm that the inclusion criteria of the SOS study are still met. DTS will be then performed and blindly evaluated by two radiologists. DTS findings will be classified based on their dimension (large axis measurement), radiological characteristics (calcific, pleural, solid, partially solid and ground glass opacity) and position (in the 5 lobes). Findings will be then classified using LUNG-RADS[1] schema and ROC analysis will be applied. Inter-observer variability will be analyzed with Krippendorff's Alpha[17].

Discordant and positive cases will be discussed in a consensus session among radiologists and thoracic surgeons. The consensus results will be used in the following analysis. The subjects with one or more nodules larger than 5 mm, not clearly benign, will undergo diagnostic contrast enhanced CT and will be followed in line with Fleischner Society[2].

5. Evaluation criteria

Lung cancer will be histologically proven, following the procedure of Pathology Division that use a double blinded analysis of biological material.

5.1. Overall survival

Overall survival (OS) defined as the time from randomization until death as a result of any cause (with at least five years of follow-up).

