21. Trial insurance	15
22. Appendix.....	15
22.1. Definitions	15
22.1.1. WHO performance status scale.....	15
22.1.2. Fleischner's society criteria	16
22.2. Technical Procedures.....	16
22.2.1. Procedure for the pathological review of diagnosis.....	16
22.2.2. Procedures for DTS examination.....	16
22.2.3. Quality of Life evaluation.....	17
22.3. References	19
23. Writing Committee and Scientific support:.....	21

Abbreviations

DTS	Digital Tomosynthesis
CT	Computer Tomography
REID	Risk of Exposure-Induced Death
BEIR	Biologic Effects of Ionizing Radiation
QoL	Quality of Life
OS	Overall Survival
LLE	Loss of Life Expectancy
ROC	Receiver Operating Characteristic
NELSON	The Dutch-Belgian Randomized Lung Cancer Screening Trial (Dutch acronym)
ICH	International Conference On Harmonisation
ECOG	Eastern Cooperative Oncology Group
EORTC	European Organisation for Research and Treatment of Cancer
CRF	Case Record Forms

Synopsis

Sponsor	Santa Croce e Carle Hospital founded by the Fondazione CRC di Cuneo
Project Title	A monocenter prospective no-profit interventional study for lung cancer early diagnosis with tomosynthesis: re-evaluation of lung nodule detection rate at 5 years
Version	July 15 th , 2017
Study Phases	Phase 3
Coordinators	[name] (study chairman), [name] (study coordinator)
Statistician	[name] (University of Torino)
Writing Committee	[name] (Nuclear Medicine Division), [name], [name] (Anatomical Pathology Division), [name], [name] (Medical Phisics Division), [name] (Oncology Division), [name] (Radiology Division), [name], [name], [name] (Thoracic Surgery Division), [name] (Pneumology Division), [name] (Health Management), [name] (Radiotherapy Division).
Population	Subjects enrolled in previously closed SOS trial (high risk subjects for lung cancer) without confirmed lung cancer.
Study Objectives	To evaluate the lung cancer detection rate in the population of high risks subjects previously enrolled in lung cancer screening trial with chest digital tomosynthesis (SOS trial).
Participating centers	Single center, Santa Croce e Carle Hospital

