Overall Study design	
The study aims to evaluate the lung cancer detection rate. Patients that previously were enrolled in SOS study will be called by project assistants and booked for DTS examination. In case the subject refuses to perform examination a phone interview for follow-up will be carried out acquiring information on the status of the subject, on the variation of quality of life, on smoke habits and on attitude toward lung cancer screening.
 
For the subject accepting the DTS examination the same questionnaire will be filled onsite just before examination. DTS will be then performed and blindly evaluated by two radiologists. DTS findings will be classified based on their dimension (large axis measurement), radiological characteristics (calcific, pleural, solid, partially solid and ground glass opacity) and position (in the 5 lobes). Findings will be then classified using LUNG-RADS [1]. The results of the DTS,in case of negative report, will be communicated with a letter to the patient.
 
The subjects with one or more nodules larger than 5 mm, not clearly benign, will undergo diagnostic contrast enhanced CT and will be followed according to Fleischner society [2] criteria.

	Discordant and positive cases will be discussed in a consensus session among radiologists and thoracic surgeons. The consensus results will be used in the following analysis.
Endpoints	
Primary
 
Lung cancer detection rate.
 
Secondary
 
 • Percentage of lung cancer addressed to radical surgery treatment; • Sensitivity of DTS evaluating the number of lung cancer occurred in the population of SOS study in the last 5 years; • Mortality • Overall survival (OS) • Quality of Life (QoL) • Cost-effectiveness
Eligibility criteria	
Inclusion criteria:
 
 • current or former smoker status; • for former smokers, the maximum time since quitting smoking must be below 10 years. • smoking history of at least 20 pack-years; • age 45-80 years; • no previous history of cancer in the 10 years before the beginning of the study; • be able to stand and hold the breath for 11 seconds during image acquisition • previous participation to SOS trial 
Exclusion criteria:
 
 • pregnancy

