Sample size	
The primary objective of this study is to calculate the detection rate on lung cancer at 5 years distance from the previous DTS. In the SOS study 1843 subjects were enrolled and lung cancer was found in 18 (0.8%) of them at baseline. 1703 subjects performed the first round DTS at one-year distance and lung cancer was found in 5 (0.3%) of them.
 
The number of patients needed to be confident that the disease will be detected if present at or above the specified prevalence of 0.3% with a confidence of 5% (i.e. assuming that the true prevalence is at least 0.3%, then a sample consisting only of subjects without lung cancer would occur 5% of the time or less given a sample with the calculated size) is 998. Allowing for a drop out of no more than 50%, a minimum number of 1496 subjects is required.

Timelines	
Expected accrual time: September 2017 / August 2018
 
Patients with positive TC will be subjected to diagnostic investigations to identify the pathology according to Fleischner Society. Length of Follow-up: no follow-up is foreseen for these patients

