Background and rationale	
Lung cancer is the leading cause of cancer-related death around the world. In 2008 there were nearly 1.6 million new cases worldwide, accounting for the 12.7% of all new cancer diagnoses[4]. Despite decreasing trends in smoking and resulting decrease in lung cancer mortality, the population at risk for lung cancer continues to be large[5]. In the past years several programs have been developed to screen for lung cancer using low-dose chest computed radiography (CT). However, only recently different studies demonstrated a clear reduction in mortality[5,6]. In particular, NLST low dose CT screening trial demonstrated a 6.7% reduction in the death rate compared to chest X-ray with a positive screening test rate for lung cancer detection of 24.2%, compared to 6.9% for conventional X-ray[7]. The use of CT as a screening test has nonetheless recently prevailed over the concern for the cost and the radiation burden[8]. Digital tomosynthesis (DTS) is a limited angle tomography that allows reconstruction of multiple image planes from a set of projection data acquired over a relatively small angle of X-ray tube movement[9]. Santa Croce and Carle Hospital has this technology from March 2010, thanks to a donation of Fondazione CRC. Although it does not have the spatial depth resolution of computed tomography, it provides high-resolution images in the sagittal planes at a lower dose and cost than CT[10]. Several studies have shown that DTS offers advantages over conventional chest X-ray and comparable of those of CT[11–13]. The Studio OSservazionale (SOS) was a clinical trial conducted within Santa Croce e Carle Hospital sponsored by Fondazione CRC analysing smokers and former smokers aged 45–80 with no cancer diagnosis. All the subjects in whom a suspicious nodule was detected by DTS underwent diagnostic CT. The SOS study demonstrated that baseline DTS detected pulmonary abnormalities in 14.5% and lung cancer in 1.0% of the subjects[14], comparable to results obtained in CT screening programs. A second DTS, within the same study, executed one year later reported pulmonary abnormalities in 0.7% and lung cancer in 0.3% of the subjects[15].

1. Background and introduction

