2.1. General objectives

To evaluate the lung cancer detection rate in the population of high risks subjects previously enrolled in lung cancer screening trial with chest digital tomosynthesis (SOS trial).

Repeating the DTS at 5 years from the baseline exam will permit to pursue three different tasks:

- 1) find subjects with lung cancer to be addressed to radical surgery treatment;
- 2) calculate the sensitivity of DTS evaluating the number of lung cancer occurred in the population of SOS study in the last 5 years;
- 3) establish the correct timing for DTS screening.

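### Overall survival is timed from a randomization that this single-cohort study does not have, and no planned follow-up supports its five-year minimum

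*Combined protocol and SAP*

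**What the plan says.** - **Definition.** Section 5.1 has OS "defined as the time from randomization until death as a result of any cause (with at least five years of follow-up"). The Synopsis lists OS and Mortality as secondary endpoints, and section 2.2 repeats both without rank.
- **Design.** Section 4 describes one cohort of about 1700 former SOS participants, each to have one DTS after completing a form "to confirm that the inclusion criteria of the SOS study are still met". Section 14 has randomization in its heading but describes only website registration at the exam. Section 18.3 mentions randomized patients and treatment allocation in passing, with no procedure behind either.
- **Population.** The Synopsis gives "Subjects enrolled in previously closed SOS trial (high risk subjects for lung cancer) without confirmed lung cancer". Section 3.1 adds "no previous history of cancer in the 10 years before the start of the study".
- **Timing.** Section 2.1 says "Repeating the DTS at 5 years from the baseline exam will permit to pursue three different tasks", whereas section 6.1.1 counts the five years from the DTS that came before. Section 6.4 plans entry from September 2017 to the end of August 2018. Section 6.3 closes the study when a year has passed, 80% of SOS participants have been contacted and the database is frozen.
- **Follow-up.** For CT-positive patients, Synopsis Timelines states "Length of Follow-up: no follow-up is foreseen for these patients". For people who decline the exam, "a phone interview for follow-up will be carried out acquiring information on the status of the subject". Section 22.2.4 lists a follow-up eCRF without a schedule.
- **Analysis.** Section 6.2 names Lung-RADS, ROC and Krippendorff's alpha. It gives no survival method, population, censoring rule or cut-off date.

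**The concern.** A survival time needs a starting point that every subject has. This one starts at an event that happens to nobody, and the five-year minimum attached to it does not fit the calendar of the new exam. The analyst would have to choose origin, population and cut-off once the data are in hand.

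The choices are not equivalent. One of them, time from the SOS baseline among people who came back, would show no deaths before the new exam simply because of how subjects enter. Mortality is no better defined. Section 10.1.2 also plans a comparison with external screening trials on lung-cancer mortality over ten years, so a badly anchored mortality figure could carry into that comparison.

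**Working it through.** **1. Is there a plan figure to reproduce?** Not for OS. The only sizing is the zero-event rule for the detection rate in section 6.1.1: the smallest n with (1 − 0.003)^n ≤ 0.05. Since 0.997^997 = 0.05001 and 0.997^998 = 0.04986, n = 998, as printed. Nothing below alters it.

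**2. Is there a randomization?** Sections 4 and 14 give one group, one exam and registration at attendance. No arms, ratio or allocation method appear anywhere.

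**3. Origin at the new DTS (reading registration for randomization).**
- Accrual, September 2017 to end of August 2018: 12 months.
- Earliest closure under section 6.3: 12 months after start.
- Follow-up at that closure: 12 − 0 = 12 months for the first entrant, 12 − 12 = 0 for the last.
- Shortfall against 60 months: 60 − 12 = 48 to 60 − 0 = 60 months.
- Five years for the last entrant: end of August 2018 + 60 months = end of August 2023, 12 + 60 = 72 months after start.

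These are calendar maxima. With no status check planned after the exam, known follow-up could be close to nil even for the first entrant.

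**4. Origin at an earlier SOS exam.**
- If five years run from baseline (section 2.1), about 5 years have elapsed at the new DTS.
- If they run from the preceding DTS (section 6.1.1), then for the 1703 people with a first-round exam one year after baseline, about 1 + 5 = 6 years have elapsed since baseline.

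The five-year minimum is then feasible, but everyone registered at the new exam has survived to it. A Kaplan-Meier curve from the SOS baseline in registered subjects, without delayed entry, stays at 100% up to the first re-examination.

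**5. Who is missing from the stated population?** The Synopsis restriction removes confirmed lung cancers. SOS reported 18 at baseline and 5 at the first round: 18 + 5 = 23, and 23/1843 = 1.25% of the SOS cohort. This is a floor, because cancers diagnosed later are not counted. It uses the printed count of 18. The 0.8% printed beside that count does not match it (18/1843 = 0.98%), but the Synopsis background gives 1.0%, which does.

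**6. Could deaths be learned of?** The status interview is for people who decline the exam, and they are alive. No section says how a death would come to light. Section 6.3 lets the study close with 80% contacted: 0.8 × 1843 = 1474.4, so 1475 suffice and up to 1843 − 1475 = 368 may never be reached. The number with unknown status could be larger, because contact (by phone in section 4, by email in section 6.4) does not guarantee an answer.

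**The case against.** The strongest defence is that randomization is a leftover template word, that OS is secondary with no hypothesis or sizing, and that the year in section 6.3 is a floor. All three conditions must hold before closure, so longer follow-up is not forbidden. That is correct as far as it goes. But the word cannot simply be replaced by registration, because the same sentence then demands five years that no section plans to observe. Follow-up of nodules under the Fleischner criteria covers only part of the cohort and is not described as survival data collection.

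A reader might infer more than the documents support:

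- *That the plan prescribes an immortal-time analysis.* It does not. It fails to exclude one, so steps 4 and 5 are a warning about one open reading.
- *That only two origins are possible.* The preceding DTS is also open, as is diagnosis among detected cancers, though no section mentions the latter as an origin.
- *That the share of SOS participants outside a registered-only analysis can be bounded.* Taking 1700 examined gives 143 of 1843 (8%); taking 998 gives 845 (46%); 50% drop-out from 1496 leaves 748, hence 1095 (59%). None of these is a forecast of attendance.
- *That rewording alone makes OS usable.* Without vital status after the new exam, neither a new origin nor delayed entry adds person-time.

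**Conclusion.** The point stands and should be fixed. OS has no usable origin, population, censoring rule or cut-off. Its five-year minimum is missed by 48 to 60 months if time runs from the new DTS and the study closes at the earliest permitted date. If time runs from an SOS exam, the minimum is reachable. In that case the starting exam is disputed between sections 2.1 and 6.1.1, and an analysis of registered subjects without delayed entry would overstate survival and leave out at least 23 known lung cancers.

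The figures assume that the section 6.4 dates hold and that the printed SOS counts are right. SOS exam dates are not in the documents, so the elapsed time is the nominal interval. Confidence is high that the origin is undefined and the follow-up unplanned. The amount of bias cannot be sized from the documents. The detection-rate endpoint and the sample size are not touched.

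**What to change.** Delete randomization from section 5.1. Before any analysis, state one origin, one population and one cut-off date for OS, and the same for Mortality. Remove the five-year minimum or restate it to match the follow-up actually planned. The choice is the sponsor's:

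- **(a) Time from the SOS baseline DTS.** Use the full SOS cohort of 1843, stated as not restricted by section 3.1 or by the Synopsis exclusion of confirmed lung cancer. Use Kaplan-Meier, censored when last known alive, and report how many have unknown status. *Cost:* a stated way to learn of deaths, and a check that consent covers non-attenders and SOS cancer cases, since section 14 registers attenders only and section 18.3 requires documented consent from everyone included. Survival is overstated if deaths are learned of less often than survival.
- **(b) Time from the new DTS in registered subjects.** Drop the five-year minimum and report the short follow-up descriptively. *Cost:* wording plus a stated vital-status check after the exam, which is new data collection.
- **(c) No vital-status collection added.** Withdraw OS as a secondary endpoint or label it exploratory. *Cost:* wording only.

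If re-examined subjects are analysed from the SOS baseline, require delayed entry at the new DTS and report survival conditional on reaching that exam. This is informative only if later vital status is collected.

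Reconcile sections 2.1 and 6.1.1 on which exam starts the five years, and reconcile the Mortality horizon with the ten-year comparison in section 10.1.2. No option changes the exams or the sample size.

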5.2. Quality of life

Related end-points are termed in the chapter on "Quality of life" (chapter 9).

5.3. Cost-effectiveness

Related end-points are defined in the Chapter on "Economic evaluation" (chapter 10).

6. Statistical considerations

6.1. Statistical design

6.1.1. Sample size

The primary objective of this study is to calculate the detection rate on lung cancer at 5 years distance from the previous DTS. In the SOS study 1843 subjects were enrolled and lung cancer was found in 18 (0.8%) of them at baseline. 1703 subjects performed the first round DTS at one-year distance and lung cancer was found in 5 (0.3%) of them.

Assuming a binomial model for the occurrence of the disease (Flanders WD and Kleinbaum DG. Basic Models for Disease Occurrence in Epidemiology, International Journal of Epidemiology, Volume 24, Issue 1, 1 February 1995, Pages 1–7) the number of patients needed to be confident that the disease will be detected if present at or above the specified annual incidence of 0.3% with a confidence of 5% (i.e. that assuming the true incidence is at least 0.3%, then a sample consisting only of subjects without lung cancer would occur 5% of the time or less given a sample with the calculated size) is 998. Allowing for a drop out of no more than 50%, a minimum number of 1496 subjects is required.

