6.3. End of study

End of study befalls when all of the next criteria have been satisfied:

1. One year after start-up
2. At least 80% of the subjects enrolled in SOS trial have been contacted
3. The database has been fully cleaned and frozen for the analysis

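### The minimum of 1496 does not leave 998 examined subjects at the 50% drop-out the plan allows: 1996 would be needed, and 1496 tolerates only a 33% loss

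*Combined protocol and SAP*

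**What the plan says.** The synopsis (Sample size) and section 6.1.1 carry nearly the same paragraph. Both require 998 subjects, so that a sample free of lung cancer would arise at most 5% of the time if the true rate is at least 0.3%. Both then add the drop-out sentence: "Allowing for a drop out of no more than 50%, a minimum number of 1496 subjects is required". Neither gives the inflation formula or defines drop-out.

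The two versions differ on what the 0.3% is. The synopsis has "if present at or above the specified prevalence of 0.3" per cent; section 6.1.1 has "if present at or above the specified annual incidence of 0.3" per cent and names a binomial model.

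Three other places bear on how many people will be examined:

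- Section 4 (Trial Design) says that "all the subjects that participated in the SOS study, will be contacted by phone", and expects about 1700 SOS subjects to have the repeat DTS.
- Section 6.3 gives three joint conditions for ending the study. The one on numbers is "At least 80% of the subjects enrolled in SOS trial have been contacted". No minimum number examined is set.
- Section 6.1.1 gives the source pool: 1843 enrolled in SOS, of whom 1703 had the one-year DTS.

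**The concern.** Drop-out ordinarily means the share of the starting number that is lost. On that meaning, a starting number that protects n completers against a loss d is n/(1 − d). The plan's figure looks like n × (1 + d), which is always too small and falls far short at d = 50%.

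This is the plan's only sample-size justification, and it concerns the primary endpoint, the detection rate. If the inflation is wrong, the stated assurance fails at a drop-out the plan presents as acceptable. The error also hides a feasibility limit: the number that would be needed is larger than the cohort from which subjects can be drawn.

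**Working it through.** **Inputs.** Rate 0.3%, probability of a cancer-free sample at most 5%, base size 998, drop-out 50%, minimum 1496, 1843 enrolled in SOS (all section 6.1.1); about 1700 expected to have DTS (section 4); 80% contacted (section 6.3).

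**1. The base figure reproduces.** The probability of no cancer among n examined subjects is (1 − 0.003)^n. Setting this to 0.05:

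n = ln(0.05)/ln(0.997) = 997.08, rounded up to 998.

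Check: 0.997^997 = 0.05001 and 0.997^998 = 0.04986. This treats 0.3% as a one-off proportion at the repeat DTS.

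**2. The 1496 reproduces only with the multiplicative form.** 997.08 × 1.5 = 1495.6, rounded up to 1496 (from the rounded 998 it would be 1497). That this is how the figure arose is an inference; the mismatch below does not depend on it.

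**3. What a 50% loss requires.**

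- Needed to keep 998: 998/(1 − 0.50) = 1996, which exceeds 1843.
- Left from 1496: 1496 × 0.50 = 748, which is 250 short of 998.
- Loss that 1496 can absorb: (1496 − 998)/1496 = 498/1496 = 33.3%.

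**4. Consequence at a one-off rate of 0.3% and a 50% loss.**

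| Starting number | Examined | Chance of no cancer |
|---|---|---|
| 1496 (stated minimum) | 748 | 0.997^748 = 10.6% |
| 1843 (all SOS enrollees) | 921 | 0.997^921 = 6.3% |
| 1700 (if only about that many are reachable) | 850 | 0.997^850 = 7.8% |
| 1475 (80% of 1843 contacted) | 737 | 0.997^737 = 10.9% |

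With 748 examined, the confidence of seeing at least one case is 100% − 10.6% = 89.4%. The lowest rate detectable with 95% confidence is 1 − 0.05^(1/748) = 0.40%.

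**5. Uptake needed for 998 examinations.** From all 1843: 998/1843 = 54.2%, so the tolerable loss is 45.8%. From 1475: 998/1475 = 67.7%. Both rise once deaths and ineligible subjects are removed; the plan does not give that number.

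**6. If 0.3% is an annual incidence.** Assume that cases accumulate over 4 or 5 years and all remain detectable at the repeat DTS. The required n is then 997.08/4 = 249.3, so 250, or 997.08/5 = 199.4, so 200. On this reading 748 would be ample, but 998 would be the wrong base figure.

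**7. A separate slip in the same paragraph.** The text has "lung cancer was found in 18 (0.8%) of them at baseline", but 18/1843 = 0.98%. The synopsis background says that SOS "detected pulmonary abnormalities in 14.5% and lung cancer in 1.0% of the subjects", which agrees with 1.0%. This does not enter the sample size.

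**The case against.** Several points can be made for the plan.

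- **1496 has no operational role.** The whole SOS cohort is invited and every eligible subject is included, so correcting the number changes neither who is approached nor what is analysed. This stands, and it limits the harm. Even so, the whole cohort with a 50% loss gives 6.3%, which still misses the stated 5%. The 10.6% and 10.9% figures apply only if invitations stop near 1496 or at 80% contacted.
- **Section 4 projects about 1700 examinations.** Read literally, that leaves a chance of no cancer of 0.997^1700 = 0.6%. But it is a projection with no minimum attached, and it cannot be squared with allowing half the subjects to drop out.
- **The denominator for drop-out is undefined.** Section 14 registers subjects at the examination, so 1496 might mean people who have already attended. Or 50% might mean losses equal to half the completers, which is the reading under which 1496 is about right. Neither meaning is stated and neither is the usual one. Taking 998 as subjects examined is an interpretation, though the natural one for a DTS detection rate.
- **On an accumulating annual incidence the sample is ample.** True under the assumption in step 6, but then 998 is wrong. On neither reading of the rate do 998, 50% and 1496 agree.

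**Conclusion.** The concern holds. With drop-out taken as the share of subjects lost, 998, 50% and 1496 cannot all be true. A 50% loss needs 1996 starters, which the SOS cohort cannot supply, and 1496 covers a loss of 33.3%. If 0.3% is the one-off rate for which 998 was calculated, the chance of a cancer-free sample at the allowed drop-out is 10.6% from 1496 and 6.3% from the full cohort, against the stated 5%. Nothing else in the plan guarantees 998 examinations.

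The effect is confined to the sizing statement. No test, stopping rule or decision uses the 5%, and no estimate is biased. It should be fixed because it is a wrong figure in the only justification of the sample size.

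**What to change.** In the synopsis (Sample size) and in section 6.1.1:

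1. Make 998 examined subjects the target, and say what drop-out is a share of.
2. Then choose one:
   - (a) keep 1496 and state that it tolerates a drop-out of at most 33%; or
   - (b) keep 50% and restate the property: 748 examined gives 89% confidence of at least one case at 0.3%, or 95% confidence at 0.40%.
3. State that 998 examinations require at least 54% of the 1843 SOS enrollees, and more after deaths and ineligible subjects are removed. Reconcile this with the 1700 or so DTS examinations expected in section 4.
4. Define the 0.3% in the same way in both places. If it is not a one-off proportion at the repeat DTS, recalculate 998.
5. Separately, correct 18/1843 from 0.8% to 1.0%.

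The cost is the wording of two paragraphs and a less favourable stated property. No extra subjects or procedures are needed.
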